7.7 Withdrawal/Termination

A subject is free to withdraw from participation in the study at any time, for any reason. An Investigator may terminate a study subject's participation in the study if:

- Any clinical adverse event (AE), laboratory abnormality, or other medical condition or situation occurs such that continued participation in the study would not be in the best interest of the subject.

- The subject meets an exclusion criterion (either newly developed or not previously recognized) that precludes further study participation.

The cause, date and time of withdrawal or termination will be documented in the source documents and in the final study report. If a subject's participation is terminated prematurely, the cause for the early termination date and time of the termination will be documented on the source documents and in the final study report.

Subjects experiencing emesis or diarrhea after dosing will be evaluated on a case-by-case basis by the PI/Sub-Investigator (to assess subject safety) and the BPSI Pharmacokinetic Scientist (for assessment of impact on PK) and the Sponsor and a decision on their continued participation will be made. All decisions will be made prior to the bioanalytical laboratory commencing bioanalysis.

Withdrawn and dismissed subjects are not required to adhere to the study specific procedures (e.g., study restrictions). If withdrawn or dismissed following administration of any drug product in the study, these subjects will be asked to adhere to the study restrictions in regards to the safety, prescription medication, over-the-counter medication, dietary and/or herbal supplements and/or teas for the expected duration of the restriction relevant to the study period the subject withdrew or was dismissed from (where that period becomes the subject's last study period).

This study may be suspended or prematurely terminated if there is sufficient reasonable cause. Written notification, documenting the reason for study suspension or termination, will be provided by the suspending or terminating party to the investigator, sponsor and regulatory authorities. If the study is prematurely terminated or suspended, the principal investigator will promptly inform the IRB and will provide the reason(s) for the termination or suspension.

Circumstances that may warrant termination include, but are not limited to:

- Determination of unexpected, significant, or unacceptable risk to subjects.
- Insufficient adherence to protocol requirements.
- Data that are not sufficiently complete and/or evaluable.
- Determination of futility.

Subjects whose participation in the study is discontinued (for any reason) will not be replaced. If a subject withdraws or is dismissed from the study, a post-study symptom-directed physical exam with the possibility for a full physical exam if deemed necessary by the PI/Sub-Investigator will be conducted and post-study testing will be completed, where possible.

8.0 STUDY PROCEDURES

8.1 Study Period Check-in Procedures

At check-in for Period 1, subjects will review the study specific ICF and document their consent by signing the ICF. At check-in for each study period, subjects will be questioned about whether they have complied with the study restrictions.

If drug therapy other than that specified in the protocol was used, a decision to continue or discontinue the subject's participation will be made by the PI/Sub-Investigator and/or by the BPSI PK Scientist and/or by the Sponsor.

Subjects will be required to provide blood and urine samples for laboratory testing (hematology, serum biochemistry and urinalysis) at check-in for each study period. For Study arm C and D blood samples will be taken on Day 3 check-in.

Urine tests for drugs of abuse and cotinine and an alcohol test will be performed on all subjects at each study period check-in. In addition, urine hCG testing will be performed on all female subjects at each study period check-in.

Clinical staff reserves the right to conduct random testing (urine drugs of abuse, cotinine, urine hCG [females only], or alcohol) on any subject at any time during the study to ensure subject compliance and/or safety. Any subjects with a positive test for urine drugs of abuse, cotinine, alcohol or urine hCG (females only) will be withdrawn immediately from the study.

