2.0 TABLE OF STUDY PROCEDURES

Procedure/Activity	Time points						
	Screening	Each Period Check-in	Period 1	Period 2	Period 3	Period 4	Post-Study
ICF	X ^a						
Drugs of Abuse	X	X					
Alcohol Test	X	X					
Cotinine	X	X					
Pregnancy (hCG) Test*	X	X					
Vital Signs (BP, HR, RR and Temperature)	X		X ^b	X ^b	X ^b	X ^b	X
Laboratory Testing	X	X [#]					X
Medical History	X						
BMI	X						
ECG	X						
Inclusion/Exclusion Assessment	X						
Restrictions Compliance Check		X	X	X	X	X	
Physical Exam	X						X
SmartPill™ Administration			X ^c	X ^c	X ^c	X ^c	
Nifedipine ER tablets Dosing (Test)			X ^d		X ^d		
PROCARDIA XL (Ref)				X ^d		X ^d	
omeprazole/sodium bicarbonate capsules Dosing					X ^e	X ^e	
pH Measurement			X ^f	X ^f	X ^f	X ^f	
PK Sampling			X ^g	X ^g	X ^g	X ^g	
Adverse Event Reporting		X ^h	X	X	X	X	X
Meals		X	X ⁱ	X ⁱ	X ⁱ	X ⁱ	

- # Laboratory testing (hematology, serum biochemistry, and urine analysis) at each period check-in for Study arm A and B on Day 1 and for Study arm C and D it will be done at check-in on Day 3.
- a- At screening and prior to any medical screening procedures.
- b- Vital signs measurements (BP, HR, RR and temperature) to be obtained for Study arm A and B, and on Day 7 for Study arm C and D at pre-dose and at 4, 12 and 24 hours after dosing nifedipine ER tablets in each study period, and at pre-dose and 1 hour after omeprazole/sodium bicarbonate capsules daily dosing (Day 1 to Day 6) in each study period for Study arm C and D.
- c- SmartPill™ capsules will be administered 30 minutes before dosing nifedipine ER tablets (Study arm A and B), and 30 minutes before dosing nifedipine ER tablets and omeprazole/sodium bicarbonate capsules (Study arm C and D) on Day 7.
- d- Study arm A and B: Nifedipine dosing on Day 2 in each study period
Study arm C and D: Nifedipine dosing on Day 7 co-administered with omeprazole/ sodium bicarbonate in each study period.
- e- Study arm C and D: omeprazole/ sodium bicarbonate capsules dosing for 7 days (Day 1 to 7) in each study period.
- f- pH will be measured at 0, 1, 2, 3, 4, 5, 6, 7, and 8 hours after SmartPill™ administration in each study period.
- g- PK sampling - Pre-dose (0 hour) and at 1, 2, 3, 4, 5, 6, 7, 8, 9, 10, 12, 16, 20, 24, 36, and 48 hours after nifedipine dosing in each study period.
- h- Pre-dose conditions at Period 1 check-in.
- i- Study arm A and B: Meals will be served at approximately 6.5, 10.5, 14.0, 24.5, 28.5, 33.5 and 37.5 hours after dosing.

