7.4 Informed Consent Procedure

The Investigator is responsible for ensuring that the informed consent is obtained before any protocol specific procedures are carried out. The decision of a subject to participate in clinical research is voluntary and should be based on a clear understanding of what is involved.

Subjects must receive adequate oral and written information. The oral explanation to the participant should be performed by the Investigator or a designated person, and must cover all the elements specified in the informed consent form.

The subject must be given every opportunity to clarify any points they do not understand and, if necessary, to ask for more information. The subject must be given sufficient time to consider the provided information. It should be emphasized that the subjects may withdraw their consent to participate at any time without loss of benefits to which they otherwise would be entitled.

The subjects should be informed and agree that their names will not be disclosed outside the site.

The Investigator or delegated member of the trial team and the subject should sign and date the Informed Consent Form to confirm that consent has been obtained. The participant should receive a copy of this document and the original should be filed in the subject binder. In case of a screen failure, it will be filed separately in the designated binder.

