7.5 Screening Procedures

Subjects will review and sign the ICF prior to medical screening procedures. Screening procedures will be conducted within thirty (30) days prior to dosing in Period 1. Screening procedures can be performed on the day of check-in prior to conducting check-in procedures. The physician (Principal Investigator (PI) or Sub-Investigator) will review all screening results/data to assess eligibility of each potential subject.

The Screening procedures will include (but is not limited to): demographic data, medical and medication histories, physical examinations, body measurements, vital signs (seated blood pressure [BP], heart rate [HR], respiratory rate [RR] and temperature.), electrocardiogram (ECG), hematology, biochemistry, serology, urinalysis, urine screening for drugs of abuse and cotinine, alcohol test and serum pregnancy test (female subjects only). For a complete listing of all tests to be performed, please refer to [Appendix B - Clinical Laboratory Assessment](#).

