11.0 SAFETY ASSESSMENT

BioPharma Services USA Inc. has established SOPs in conformity with regulatory requirements to ensure the timely, accurate and complete reporting of safety information.

PI/Sub-Investigators at BPSUSA are responsible for monitoring the safety and for providing appropriate medical care for subjects who have entered this trial (i.e., from the signing of ICF onwards). In addition, the PI/Sub-Investigator remains responsible for following-up all AEs.

Each subject will be carefully questioned and/or examined by the PI/Sub-Investigator or a medically qualified delegate (i.e., authorized by the Investigator, in a separate form, to record AEs) to obtain information regarding AEs. All AEs will be reported and documented as stated below

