14.3 Informed Consent Form

Subjects will sign the ICF prior to starting any screening procedures. Each subject will be provided with verbal and written information, in non-technical terms, which will describe the nature of the screening procedures as well as conduct of the study. Prior to signing the ICF, subjects will be allowed adequate time to consider the potential benefits and risks associated with their participation in the study. Signed and dated ICFs will be retained with the study records and a copy will be provided to the subject.

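### Section 8.1 and the Appendix A ICF row put consent at Period 1 check-in, against Sections 2.0, 7.4, 7.5 and 14.3, which require it before screening

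*Combined protocol and SAP*

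**What the plan says.** Four places put the signature first.

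- Section 2.0, Table of Study Procedures, marks the ICF under Screening. Footnote a reads "At screening and prior to any medical screening procedures".
- Section 7.4 makes the investigator responsible for seeing that "informed consent is obtained before any protocol specific procedures are carried out".
- Section 7.5 opens with "Subjects will review and sign the ICF prior to medical screening procedures".
- Section 14.3 states "Subjects will sign the ICF prior to starting any screening procedures", and describes subject information that covers both screening and the conduct of the study.

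Two places put it later.

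- Section 8.1 begins "At check-in for Period 1, subjects will review the study specific ICF and document their consent by signing the ICF".
- Appendix A leaves the ICF row empty under Screening and marks it on Day 1 of the arm A and B block and on Day 1 of the arm C and D block.

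On the length of screening, Section 7.5 says "Screening procedures will be conducted within thirty (30) days prior to dosing in Period 1", and also "Screening procedures can be performed on the day of check-in prior to conducting check-in procedures". Appendix A heads its screening column Day -28 to 0.

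**The concern.** The protocol gives two different times for one act, and the later one falls after procedures that need consent. In Appendix A the Screening column carries the physical examination, ECG, serology for HIV and hepatitis B and C, hematology, chemistry, urinalysis, and the drug, alcohol, cotinine and pregnancy tests. The same column has no ICF mark. A coordinator who works from that schedule, or from the check-in procedure in Section 8.1, is told to test first and obtain the signature afterwards.

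What is at stake is a participant-protection rule that the protocol states clearly elsewhere. The revision history shows that the sponsor had seen the problem. The August 2017 version moved the ICF to Screening in Section 2.0, with the stated aim of removing ambiguity about when consent is obtained. Section 8.1 and Appendix A still carry the Period 1 timing. That history is context only: the conflict exists within the current text.

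**Working it through.** No power, sample-size or error-rate figure bears on this. The check is a comparison of the texts and a count of days.

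**Step 1. Is it a true conflict?** Section 8.1 has subjects sign at Period 1 check-in. Section 7.5 has them sign before medical screening, and allows screening on the check-in day only if it comes before the check-in procedures. So even with same-day screening the order differs: Section 7.5 gives consent, screening, check-in, while Section 8.1 read literally gives screening, then consent at check-in.

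**Step 2. Is the Appendix A row a table-reading error?** Unlikely. Its two marks fall on the same Day 1 columns as check-in marks, the history, ECG and serology rows are correctly filled under Screening, and Section 8.1 gives the same late timing in prose.

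**Step 3. How long could testing precede consent under the late timing?** The gap is the earliest permitted screening day to the day of signature. Consent is taken as Day 1, where Appendix A puts it, and dosing in Section 7.5 as the first dose of any study drug.

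| Case | Calculation | Longest gap |
|---|---|---|
| Section 7.5 window, Period 1 is arm C or D (omeprazole starts Day 1) | 30 - 0 | 30 days |
| Section 7.5 window, Period 1 is arm A or B (nifedipine on Day 2) | 30 - 1 | 29 days |
| Appendix A window, Day -28 to Day 0 | 0 - (-28) | 28 days, or 29 to Day 1 if Day 0 is a separate day |
| Screening on the day of check-in | same day | 0 days |

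The range is therefore 0 to about 28 to 30 days.

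**Step 4. Who signs?** Under Section 8.1 only people who arrive for Period 1 check-in sign. Someone screened earlier and found ineligible would not. Section 7.4 says that in a screen failure the original consent form is filed in a separate binder, which presupposes a signed form. Inclusion criterion 5 in Section 7.2 also speaks of written consent before any study procedure. Both fit the early timing and not the late one.

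**The case against.** The strongest reply is that the protocol as a whole leaves little doubt. Sections 2.0, 7.4, 7.5 and 14.3 and inclusion criterion 5 all point to early consent, Section 7.5 is the text that governs screening, and Section 8.1 covers check-in only. A site could act on Section 8.1 alone only by going against the rest. This stands: it makes the consequence conditional and shows which side is to be corrected. It does not remove the conflict, because Appendix A is a schedule in its own right and contradicts the one in Section 2.0.

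A second reply is that the phrase study specific ICF in Section 8.1 may mean a further review or signature after a separate screening consent. The consent pages are not in the file, so this cannot be excluded. But the protocol text describes no separate screening consent, and Section 14.3 describes one form covering both stages. Even on this reading, Appendix A would lack the screening signature.

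A reader might infer several stronger points that the documents do not support.

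- **All the working schedules carry the late timing.** They do not. Section 2.0 is also a working schedule and has the early timing.
- **Subjects would have to follow medication or contraception rules before agreeing to take part, because of this conflict.** Same-day screening is allowed, so the 14-day and 30-day look-back rules can precede consent under either timing.
- **Safety reporting has a gap.** Section 11.0 does run investigator responsibility "from the signing of ICF onwards", but Appendix A marks adverse events at Screening. Sections 11.1 and 11.3 tie adverse events to study drug administration, so under those definitions pre-dose events fall outside whenever the form is signed.
- **Data would have to be discarded.** No section states such a rule.

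**Conclusion.** The contradiction is real and should be corrected. Section 8.1 and the Appendix A ICF row are out of line with Sections 2.0, 7.4, 7.5 and 14.3, and the protocol's own text shows that the early timing is intended. If the late timing were followed, screening tests would precede consent by 0 to about 28 to 30 days, and screen failures might never sign.

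The size of the gap rests on the two assumptions in the working: consent on Day 1, and the Section 7.5 window counted back from the first dose of any study drug. If that window were instead counted back from nifedipine on Day 7 in arms C and D, the longest gap there would be 30 - 6 = 24 days. Neither assumption affects whether the texts conflict.

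The documents do not show that any volunteer was or would be tested before consent. The finding is that two places instruct it. Dosing, blood sampling for pharmacokinetics and gastric pH all come after Period 1 check-in, or after the Day 1 ICF mark, so no endpoint, analysis set or estimate changes under either timing.

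**What to change.** 1. In Section 8.1, replace the first sentence with a check at Period 1 check-in that the ICF signed at screening is on file. If a second review is intended, say that consent is re-confirmed at that point.
2. In Appendix A, move the ICF mark from Day 1 of both arm blocks to the Screening column.
3. Optionally, state one screening window in the same edit. The 28 days of Appendix A fit inside the 30 days of Section 7.5, so this is tidying and not a second contradiction.

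The cost is one sentence and one table row. No procedure is added, and sample size and analysis are untouched. Section 15.1 already has a route for correcting discrepancies, which includes submission to the IRB.

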8.2 Food and Fluid Intake

SmartPill™ Administration, Study arm A and Study arm B

Following at least an 8-hour overnight fasting period, subjects will be dosed with nifedipine ER tablets and will be required to continue to fast for at least 6 hours after dosing.

Following the fasting period of at least 6-hours after dosing, subjects will be given standardized meals and caffeine/methylxanthine-free beverages at scheduled times. In this study, meals will be served at approximately 6.5, 10.5, 14.0, 24.5, 28.5, 33.5, and 37.5 hours after dosing. Meals and beverages during confinement will be identical for all study periods.

Except for water given with study medication, no fluid will be allowed from 8 hours before dosing until 6 hours post-dose. Water will be allowed up to ½ cup (4 fl. oz.) during the six (6) hours post-dose and then water will be allowed/provided *ad libitum* at all other times.

Study arm C and Study arm D

No food will be allowed from at least 8 hours before dosing of omeprazole/sodium bicarbonate capsules from Day 1 to Day 6 until at least 1 hour after dosing. Following the administration of omeprazole/sodium bicarbonate capsules on Day 6, subjects will be required to fast for at least an 8-hour overnight fasting period before dosing of nifedipine together with omeprazole/sodium bicarbonate capsules on Day 7, and will continue to fast for at least 6 hours after dosing.

Subjects will be given standardized meals and caffeine/methylxanthine-free beverages at scheduled times during their confinement. In this study, meals will be served at approximately 4.5, 9.5, 13.5, 24.5, 28.5, 33.5, 37.5, 48.5, 52.5, 57.5, 61.5, 72.5, 76.5, 81.5, and 85.5 hours after capsules dosing on Day 3. Following the fasting period of at least 6-hours after dosing of nifedipine together with omeprazole/sodium bicarbonate capsules on Day 7, subjects will be given standardized meals and caffeine/methylxanthine-free beverages at approximately 6.5, 10.5, 14.0, 24.5, 28.5, 33.5, and 37.5 hours after dosing. Meals and beverages during confinement will be identical between each study period.

On dosing Day 1 to Day 6, except for water given with study medication, no fluid will be allowed from 1 hour before dosing and 1 hour post-dose. Water will be allowed/provided *ad libitum* at all other times. On Day 7, except for water given with study medication, no fluid will be allowed from 8 hours before dosing until 6 hours post-dose. Water will be allowed up to ½ cup (4 fl. oz.) during the six (6) hours post-dose and then water will be allowed/provided *ad libitum* at all other times.

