Study arm C and D: Meals will be served at approximately 4.5, 9.5, 13.5, 24.5, 28.5, 33.5, 37.5, 48.5, 52.5, 57.5, 61.5, 72.5, 76.5, 81.5 and 85.5 hours after omeprazole/sodium bicarbonate capsules dosing on Day 3. Meals will be served at approximately 6.5, 10.5, 14.0, 24.5, 28.5, 33.5, and 37.5 hours after dosing on Day 7.

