3.2 Rationale

The current research proposal is funded by the FDA via a contract agreement (HHSF 22320161004I) with the purpose of investigating the in vivo performance consistency of oral MR drug products under the effect of an elevated gastric pH environment (e.g. co-administration of PPIs). We have chosen to focus on nifedipine ER tablets (brand name and generic products) because the RLD is an osmotic pump and there is a generic version commercially available as matrix-based formulations. We will evaluate the bioequivalence in an open label, clinical study with and without multiple-dose PPI co-administered with the brand name drug and a generic version. In the current study, clearance, volume of distribution, and absorption, as determined by physiological variables (e.g. gastric emptying, motility, pH), are assumed to have less inter-occasion variability compared to the variability arising from formulation performance within the same subject [6, 12-14]. Therefore, differences between two products because of formulation factors can be determined [15].

This clinical study will be open-label because blood concentration levels cannot be influenced by knowledge of the identity of treatment, however, the laboratory analysts will be unaware of the study product sequences. The period of 48 hours, over which blood samples will be collected, is considered to be sufficiently long to adequately characterize the concentration-time profile of extended-release nifedipine (the mean half-life of nifedipine is less than 10 hours). It has been shown that administering multiple-dose (e.g. 7 days) PPIs (i.e. omeprazole) in healthy volunteers can effectively increase their gastric pH [16, 17]. In the current clinical study, subjects will be dosed with PPIs in the first two days without confinement (i.e. outpatient visits) to reduce their burden. Dosing the subjects with PPIs in confinement for the last 5 days is deemed necessary in order to standardize the food effect (omeprazole administration under fasting conditions) prior to the PK study of nifedipine ER tablets. Since the omeprazole PD effect can be eliminated after 3-5 days of discontinuing the drug, a wash-out period of at least 7 days is sufficient to allow the complete elimination of the drug before subsequent dosing and to avoid carry-over effects. In this study, a wash-out period of at least 14 days is chosen to ensure the scientific and logistic conduct of the study.

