Nifedipine (Procardia XL®, Pfizer) is a cardiovascular drug that is used for the long-term treatment of hypertension and angina. Nifedipine is a weak acid (pKa 3.9) which is practically insoluble in water and has a pH-dependent solubility across pH 1-7. According to the Biopharmaceutical Classification System (BCS), it is a Class II compound with an oral bioavailability determined by aqueous solubility.

Nifedipine (Procardia XL®) was approved by the FDA in 1989. After loss of patent protection, the FDA approved several generic nifedipine ER tablets manufactured by Osmotica (2005), Mylan (2010), Matrix Laboratories (2010), and others. Although several *in vivo* and *in vitro* methods are available to measure product bioavailability and bioequivalence for orally administered drug products, the FDA guidelines recommend reliance on pharmacokinetic measures such as the rate (i.e., maximum concentration [C_{max}]) and extent (i.e., area under the concentration-time curve [AUC]) of absorption as these best reflect systemic exposure(<http://www.fda.gov/downloads/drugs/guidancecomplianceregulatoryinformation/guidances/ucm320010.pdf>). Nifedipine should be administered orally and may be given with or without food [6]. Omeprazole/sodium bicarbonate should be taken orally on empty stomach at least one hour before meal². Therefore, the investigational medicinal products (IMPs) will be administered orally under fasting conditions to better distinguish possible differences between the IMPs. This is in compliance with the Guidance for Industry [15].

The specific aim of this research is to conduct a randomized, single-dose, four-treatment, four-period cross-over *in vivo* bioequivalence study in 65-66 healthy adult volunteers (males and non-gravid females) (The sample size is discussed in [Section 7.1](#) of this Study Protocol) to evaluate the *in vivo* performance of brand and generic nifedipine ER tablets with or without co-administration of multiple-dose PPIs. The pharmacokinetics of nifedipine as Procardia XL® and generic nifedipine ER tablets, Procardia XL® with PPIs and generic nifedipine ER tablets with PPIs will be determined and compared in healthy volunteers under fasting conditions.

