The products will be studied using a crossover design with 65-66 healthy, non-smoking male and non-pregnant female volunteers being administered an oral dose of 1 × 60 mg extended-release tablet with or without co-administration multiple-dose of omeprazole / sodium bicarbonate, 1 x 40 mg/1100 mg once daily for 7 consecutive days under fasting conditions (i.e. subjects are dosed every 24 hrs). There will be at least a 14-day washout after Nifedipine only dosing (Study arms A or B) and for Study arms C and D (e.g., omeprazole/sodium bicarbonate followed with Nifedipine), at least 14 days after the last dose with omeprazole/sodium bicarbonate until the next study arm dose. Blood samples will be collected at pre-dose (0 hour) and at 1, 2, 3, 4, 5, 6, 7, 8, 9, 10, 12, 16, 20, 24, 36, and 48 hours after nifedipine dosing for Study arm A and B on Day 2 and on Day 7 for Study arm C and D in each study period.

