7.6 Study Restrictions

If any subject does not comply with these restrictions, at any time prior to or during the study, continued participation will be re-assessed by the PI/Sub-Investigator, BPSI PK Scientist and/or the Sponsor.

1. No food will be allowed from at least 8 hours before dosing until at least 6 hours after dosing (Study arm A and B). Following the administration of omeprazole/sodium bicarbonate capsules on Day 6, subjects will be required

to fast for at least an 8-hour overnight fasting period before dosing of nifedipine together with omeprazole/sodium bicarbonate capsules on Day 7, and will continue to fast for at least 6 hours after dosing (Study arm C and D). Except for water given with study medication (nifedipine, omeprazole/sodium bicarbonate, SmartPill™), no fluid will be allowed from 8 hours before dosing until 6 hours post-dose. Water will be allowed up to ½ cup (4 fl. oz.) during the six (6) hours post-dose and then water will be allowed/provided *ad libitum* at all other times.

2. For Study arm C and D, no food will be allowed from at least 8 hours before dosing of omeprazole/sodium bicarbonate capsules from Day 1 to Day 6 until at least 1 hour after dosing. Except for water given with study medication, no fluid will be allowed from 1 hour before dosing and 1 hour post-dose. Water will be allowed up to ½ cup (4 fl. oz.) during the six (6) hours post-dose and then water will be allowed/provided *ad libitum* at all other times.
3. Subjects will be required to abstain from smoking or use of tobacco products from 6 months prior to the first study period and for the entire duration of the study based on self-reporting and the cotinine test.
4. Use of any enzyme-modifying drugs and/or other products, including strong inhibitors of cytochrome P450 (CYP) enzymes (e.g., cimetidine, fluoxetine, quinidine, fluconazole, itraconazole, clarithromycin, erythromycin, nefazodone, saquinavir, indinavir, and nelfinavir) and strong inducers of CYP enzymes (e.g., barbiturates, carbamazepine, glucocorticoids, phenytoin, St. John's Wort and rifampicin) within 30 days prior to first study period until the last blood draw in the final study period.

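### In arms C and D the first meals on Days 4, 5 and 6 are scheduled 30 minutes after the PPI dose, although the protocol bars food for at least 1 hour after it.

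*Combined protocol and SAP*

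**What the plan says.** **Meal schedule.** In Section 8.2, under Study arm C and Study arm D, meals are served at about 4.5, 9.5 and 13.5 h and then at "24.5, 28.5, 33.5, 37.5, 48.5, 52.5, 57.5, 61.5, 72.5, 76.5, 81.5, and 85.5 hours after capsules dosing on Day 3". Footnote i of the Table of Study Procedures (Section 2.0) carries the same list, ending "72.5, 76.5, 81.5 and 85.5 hours after omeprazole/sodium bicarbonate capsules dosing on Day 3".

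**Dosing interval.** Section 5.1 states "i.e. subjects are dosed every 24 hrs". The worked example in Appendix A gives 7:30 AM for every PPI dose.

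**Food rule.** Section 7.6 item 2 allows no food from at least 8 hours before dosing of the "capsules from Day 1 to Day 6 until at least 1 hour after dosing". Section 8.2 has the same rule in the paragraph before the meal list.

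**Fluid rule.** For Days 1 to 6, Section 8.2 says that, apart from dosing water, "no fluid will be allowed from 1 hour before dosing and 1 hour post-dose". The scheduled meals come with beverages.

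**Reason for the rules.** Section 3.2 says the PPI "should be taken orally on empty stomach at least one hour before meal". It justifies confining subjects for the last five PPI days as "deemed necessary in order to standardize the food effect (omeprazole administration under fasting conditions".

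**The concern.** The meal list and the fasting rule are both instructions to the clinic, and they appear to conflict on three days of each PPI period. Followed literally, the meal list gives subjects breakfast half an hour after the Day 4, 5 and 6 capsules. The Day 3 capsule is followed by 4.5 h without food, so doses within one confinement would be taken under different post-dose food conditions. Confinement is there to make those conditions uniform.

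What is at stake is the consistency of the PPI pretreatment, and whether routine conduct is recorded as a deviation. Under Section 7.6, a subject who breaks a restriction has continued participation reassessed, so a schedule that itself breaks the restriction is awkward to run and to document.

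**Working it through.** **Inputs**

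- Dose times, with the Day 3 capsule as 0 h and a 24 h interval (Section 5.1): Day 3 = 0, Day 4 = 24, Day 5 = 48, Day 6 = 72, Day 7 = 96 h.
- Meal times: the 15 values in Section 8.2, repeated in footnote i.
- Rules for Days 1 to 6: food no sooner than 1 h after the dose, and none for at least 8 h before it (Sections 7.6 and 8.2). Day 7 also requires an overnight fast of at least 8 h.

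**Post-dose check:** gap = meal time − time of the preceding dose; pass if the gap is at least 1 h.

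| Day | Dose (h) | Meals (h) | Gaps (h) | Result |
|---|---|---|---|---|
| 3 | 0 | 4.5, 9.5, 13.5 | 4.5, 9.5, 13.5 | all pass |
| 4 | 24 | 24.5, 28.5, 33.5, 37.5 | **0.5**, 4.5, 9.5, 13.5 | first fails |
| 5 | 48 | 48.5, 52.5, 57.5, 61.5 | **0.5**, 4.5, 9.5, 13.5 | first fails |
| 6 | 72 | 72.5, 76.5, 81.5, 85.5 | **0.5**, 4.5, 9.5, 13.5 | first fails |

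Three meals fail and 12 pass. Each failing gap is half the stated minimum.

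**Pre-dose check:** gap = dose time − last earlier meal; pass if at least 8 h.

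- Day 4: 24 − 13.5 = 10.5 h
- Day 5: 48 − 37.5 = 10.5 h
- Day 6: 72 − 61.5 = 10.5 h
- Day 7: 96 − 85.5 = 10.5 h

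All pass.

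**Could dosing move instead?** To leave 1 h before the listed meals, the capsules would have to be given by 24.5 − 1 = 23.5 h, 48.5 − 1 = 47.5 h and 72.5 − 1 = 71.5 h. That departs from the 24 h interval and the 7:30 AM example.

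**Day 7.** The first meal is 6.5 h after dosing, outside the 6 h post-dose fast, so there is no conflict.

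**Extent.** 3 doses × 2 PPI periods = 6 doses per subject. If the list were followed literally throughout, that is 6 × 52 = 312 administrations among the minimum 52 completers, and at most 6 × 65 = 390 to 6 × 66 = 396 among all enrolled.

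**The case against.** The arithmetic is not in dispute. The case against is about weight.

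- **Only pretreatment is touched.** No nifedipine dose, blood sample or pH reading falls on Days 4 to 6. On Day 7 the capsule is taken fasted and gastric pH is measured directly, so inadequate acid suppression should be visible. This stands.
- **The capsules are still taken fasted.** Each confined dose from Day 4 on follows a 10.5 h fast, and the same meal list applies in both PPI arms. Only the post-dose hour fails, and C versus D remains a like-for-like comparison. This stands.
- **Absorption is fast.** Section 3.3 gives a time to peak of about 30 minutes (range 10 to 90) when the product is taken 1 hour before a meal. A meal at 0.5 h therefore arrives around the typical peak, though before it in slower absorbers. The reduction of about 24% in omeprazole AUC reported there is for dosing 1 hour after a meal, which does not occur here. This points to a small effect but does not size it, because no figure is given for a meal 30 minutes after dosing.
- **Meal times are approximate and the fasting rule is a firm minimum.** Staff could let the minimum govern and hold breakfast. That is a sensible way to cope, but the protocol does not say which instruction prevails. A nominal 30 minutes, repeated on three days in two places, is more than service tolerance around a 1-hour minimum.
- **The fluid rule is less clear than the food rule.** Section 7.6 item 2 also allows up to half a cup of water in the six hours post-dose. That leaves the water rule ambiguous, but it does not permit a meal or other beverages. The food rule carries the point alone.
- **Counting administrations inflates one scheduling slip.** The informative figure is three meal times in a list that appears twice; the counts above show only how often it would recur.

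**Conclusion.** The concern holds. With dosing every 24 h, three of the 15 scheduled meals in each PPI period fall 0.5 h after a capsule, against a required minimum of 1 h, and nothing in the documents reconciles the two. This affects three of the six pretreatment doses in each of arms C and D.

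The conclusion rests on the 24 h interval in Section 5.1 and on reading the meal times at their nominal values. It makes no claim about the size of any effect on omeprazole exposure, gastric pH or nifedipine pharmacokinetics. The documents do not allow that calculation, and the effect is probably small. The inconsistency should be corrected because it governs what the clinic does, but it does not threaten the main comparisons.

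**What to change.** In Section 8.2 and in footnote i of the Table of Study Procedures, move the first meals on Days 4, 5 and 6 to no earlier than 25, 49 and 73 h after the Day 3 capsule, with the same times in both PPI periods. For example, 25.5, 49.5 and 73.5 h give 1.5 h after each dose and 3.0 h before the next meal (28.5 − 25.5 = 52.5 − 49.5 = 76.5 − 73.5 = 3.0). The other 12 times can stay, and all 15 then satisfy both the post-dose and the pre-dose rule.

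The cost is a protocol clarification of three meal times in two places. Blood sampling, sample size and analysis are unaffected.
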